7.1 Study Procedures/Evaluations

7.1.1 Study Specific Procedures

Patients meeting inclusion criteria will be randomized at their preoperative appointments with a sealed envelope method and an initial evaluation will be completed for pre-operative pain levels using the numerical pain rating scale. At the conclusion of their respective surgery just prior to wound closure, the appropriate medications will be topically administered into the wound and the wound will be closed via standard method. Patients will record pain scores at home daily and also record the amount of pain pills (Norco 5/325mg) needed postoperatively until post operative day 14.

Preoperative analog pain scoring will be performed followed by postoperative analog pain scoring on postoperative day 0-14. Compliance will be recorded by the patient in a written form. Number of opioid pain medications taken will also be recorded by patient in a written form.

Analog pain scoring preoperatively on day of surgery and postoperatively day of surgery. Pain scale from 0 (no pain) to 10 (highest level of pain ever experienced). This scoring system will also be utilized by the patient daily until postoperative day 14.

Opioid prescriptions (Norco 5/325 mg) will be given to patients post operatively. Total number of pills taken up until post operative day 14 will be recorded by the patient.

This will allow us to track the patients relative pain pre and postoperatively until postoperative day 14.

- Medical history will be obtained in hand surgery clinic at initial patient presentation.

CONFIDENTIAL

This material is the property of the NYU School of Medicine and Langone Medical Center. Do not disclose or use except as authorized in writing by the study sponsor
Interventional Template Version: 11 January 2019

- Medication history will include details about the specifics of their hand problem along with a past medical history that includes history of chronic pain, narcotic addiction, recreational drug dependency, psychiatric pathologies, allergy to drugs and preferences for anesthesia. Those patients who only wish to have an anesthetic upper extremity block performed by anesthesia will not qualify for the study.
- Physical examination will consist of a full hand examination. The most important criteria will be the presence or absence of an already open wound prior to surgical intervention.

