- The patients will be counseled on the study objectives and methods of data collection. The numerical pain rating scale will be explained in detail to the patient.
- The patients will be administered a pain diary in which they will be able to log their daily pain level at the same time each day (AM) based on the numeric pain scale (1-10). They will also be instructed to log their pain medication usage and the number of pills of Norco 5/325 mg that are consumed. This log will continue daily for a total of 14 days postoperatively.

The first visit will be the initial evaluation of the patient when they present for their individual hand surgery evaluation. If they qualify for their study, an initial preoperative pain scale will be used to assess their pain level.

The next assessment will be on the day of surgery. The patient will be evaluated in the preoperative holding area and another pain level evaluation will be done for a POD#0 timepoint.

The patient will be evaluated in PACU for total time in PACU.

Each patient will receive their log book and take it home with them. The patients will be called on each day by the study team to ensure that they have been logging their daily pain score. The study team will call the patient for this purpose.

The patients will be seen in person on their first postoperative visit (approximately 1-2 weeks later). If this is prior to postoperative day 14, they will follow up again in hand clinic after day 14 (in 4-6 weeks post-surgery) to submit their log books.

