7.2 Study Schedule

Screening/Baseline Visit (up to 3 months prior to day of surgery)

- Obtain informed consent of potential participant verified by signature on written informed consent for screening form.
- Review medical history to determine eligibility based on inclusion/exclusion criteria.
- Review medications history to determine eligibility based on inclusion/exclusion criteria.
- Perform medical examinations needed to determine eligibility based on inclusion/exclusion criteria.
- Schedule day of surgery where primary intervention will be performed.
- Provide participants with information regarding tranexamic acid, and operative steps for administration of drugs into surgical wound prior to closure.
- Provide participants with log books.
- Randomize patient using sealed envelope method.

Day of Surgery

- Verify patient still meets inclusion/exclusion criteria.
- Administer study treatment
- Patient fills out Day 1 of pain diary

Intermediate Visits

- Participants will be called via phone each day by the study team to ensure they have completed their daily log of numerical pain rating scale and number of pain pills taken.
- They will arrive for an intermediate visit on their first postoperative visit (variable time, between 3-14 days postoperatively). Log books will be collected only after postoperative day 14.

Final Study Visit (up to 6 weeks post surgery)

CONFIDENTIAL

This material is the property of the NYU School of Medicine and Langone Medical Center. Do not disclose or use except as authorized in writing by the study sponsor
Interventional Template Version: 11 January 2019

Pain logs will be collected from participants who have not already returned them to study staff. The participants will be released of their duties to the study once the log books have been returned to the physicians. They will continue their routine follow up per the follow up schedule for each hand surgery procedure. No additional data is collected for study purposes at post-op visits beyond data collected per standard of care.

8 Assessment of Safety

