10.1.2 Analysis of the Primary Efficacy Endpoint(s)

Data will be expressed either as a mean (SD) or median and interquartile range (IQR). To evaluate PACU time as a function of each group, a one way analysis of variance test followed by a Tukey-Kramer post hoc test will be performed. To assess the number of pain pills need as a function of each group, a Kruskal-Wallis test followed by a Dunn post hoc analysis will be performed. To compare pain levels between the treatment arms, pain scores on a scale of 1 (lowest aka no pain) to 10 (highest pain experienced in life) will be collected daily via a patient log. They will be analyzed as a change from baseline (preoperative) pain levels and analyzed used a series of two proportion z tests with a family error rate equal to 0.05. For all tests, a P value of less than 0.05 will be considered statistically significant.

Pain is a subjective measure. We will be using an analog pain scale and reference them to the patients pre and postoperatively to account for this. Patients may take over the counter pain medication postoperatively. We cannot control the patient's use of over the counter pain medications while at home, thus we will have to rely on their accuracy and honesty for this study.

Patients will be called daily to ensure completion of daily log books. If they are not able to do this, they will be removed from the study analysis. If the patients return to clinic at 4-6 weeks post-surgery and they have completed their logs, their data will still be accepted. But if there is missing data, they will be removed from the analysis.

11 Source Documents and Access to Source Data/Documents

All data will be stored on HIPAA compliant and encrypted REDCap, approved by the institution and managed by MCIT.

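### The daily calls record no values and the diary has no entry deadline, so the plan cannot tell same-day pain scores from recalled ones

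*Combined protocol and SAP*

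**What the plan says.** **The record.** Section 7.1.1 has the patient write down a pain score and the number of opioid tablets each day to postoperative day 14, with pain scored at the same time every morning. On adherence it says: "Compliance will be recorded by the patient in a written form".

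**The call.** It is described three times:
- Section 7.1.1: "The patients will be called on each day by the study team to ensure that they have been logging their daily pain score".
- Section 7.2: patients are phoned "to ensure they have completed their daily log of numerical pain rating scale and number of pain pills taken".
- Section 10.1.2: "Patients will be called daily to ensure completion of daily log books".

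**Custody of the log.** Section 7.2 states: "Log books will be collected only after postoperative day 14". Under Section 7.1.1, a patient whose first postoperative visit falls before day 14 hands the log in at 4-6 weeks.

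**Who is analysed.** Section 10.1.2 first drops patients who cannot do what the calls are meant to ensure. It continues: "If the patients return to clinic at 4-6 weeks post-surgery and they have completed their logs, their data will still be accepted". The next sentence drops any patient with missing data. The pain scores are analysed as change from the preoperative level, and the number of pills is compared between arms with a Kruskal-Wallis test.

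**The concern.** The plan asks for a same-day measurement, taken each morning, but its acceptance rule looks only at whether the log is complete when it comes back. A patient who missed some days has two options: leave the blanks and be dropped, or fill them from memory and be kept. The rule favours the second, and a plausible late value looks like any other.

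The primary endpoint is the pain comparison, and its postoperative home scores have no other source in the protocol. A recalled score may reflect how the patient feels at the time of writing or how the recovery went, rather than the pain on the day. Section 2.4.2 puts the interest in the immediate postoperative period, and those entries would be the oldest if filled in late. The contact that could prevent this is already planned for every day, but it is not used to capture a value.

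**Working it through.** The plan states no figure on this point, so there is none to reproduce. The check is a comparison of sections plus simple subtraction.

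**1. Does any call capture a value?** All three descriptions give the purpose as completion of the log. None says that the caller asks for, records or dates a score or a pill count.

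**2. Does anything limit when an entry is made?** Section 7.1.1 sets the intended time (each morning) but no latest time. Sections 11 and 14.1 require corrections to be initialled and dated; that covers changes to an existing entry, not the time of first entry. The quality checks in Section 12 target missing or anomalous values, and a plausible late value is neither. No section reconciles the log with the calls.

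**3. How does Section 10.1.2 treat three logs handed in at 4-6 weeks?**

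| Log | Result under the stated rules |
|---|---|
| Every entry made on its own day | Accepted |
| Some entries filled in later from memory, no blanks | Accepted, with nothing specified to distinguish it from the first |
| Same missed days, left blank | Patient removed |

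**4. How old could an entry be?** Age = hand-in day minus diary day, counting postoperative days, with 4-6 weeks taken as day 28 to day 42.
- Day-1 entry: 28 − 1 = 27 days; 42 − 1 = 41 days.
- Day-14 entry: 28 − 14 = 14 days; 42 − 14 = 28 days.

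These are worst-case ages, for an entry first made at the visit.

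**5. What does removal cost?** Each arm has 10 patients, so one removal is 1/10 = 10% of an arm. Section 5.6 expects about 40 enrolled to give 40 evaluable, an allowance of 40 − 40 = 0.

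**6. What contact is already planned?** 40 patients × 14 days = 560 calls if every call is made. The documents give no contact rate, so the number that would yield a value is unknown.

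**7. Which endpoints are touched?** The diary pain scores are. The pill count is too, but differently: Sections 4.2.2 and 10.1.2 use the number of pills, not a by-day series, so the risk is a misremembered total. PACU time and the preoperative scores taken by staff are not affected.

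**The case against.** The strongest reply is that the acceptance sentence concerns late hand-in, not late entry. Section 7.1.1 makes 4-6 weeks the ordinary return point for anyone first seen before day 14, and Section 7.2 collects outstanding logs at the final visit. That reading is fair. A reader might infer that the plan approves of back-filling, or that logs returned at 4-6 weeks were filled in then; the text supports neither. It is silent on when entries were made, and that silence is the weakness.

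Second, the daily calls are a real prompt. For a patient who is reached and answers truthfully, the next call would normally hold the delay to about a day, so ages of several weeks need someone unreachable or misreporting throughout. This stands, and it is why the ages above are a worst case only.

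Third, Section 10.1.2 also drops patients who are unable to comply with the daily logging. That rule is ambiguous (not reachable, or not logging), and on either reading the sentence after it readmits a patient whose log is later complete.

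Fourth, if the patients are the blinded party, recall error might mainly add noise or dilute differences rather than favour an arm. That is possible, but the protocol says only that the trial is single-blinded, not who is blinded. Dilution would still matter with 10 patients per arm.

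Finally, the diary form, case report form and call log are not in the documents. One cannot say that no record anywhere would show entry times, only that the protocol specifies none.

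**Conclusion.** The point holds as a gap in data capture. The protocol phones patients every day without having the caller record a value, sets no latest time for a diary entry, accepts a log found complete at 4-6 weeks, and removes anyone with a gap. Under these rules recalled scores can enter the primary analysis unrecognised, and the removal rule encourages it.

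The size is bounded but not estimated. The worst-case age of an entry is 27-41 days for day 1 and 14-28 days for day 14, assuming first entry at a day 28-42 visit. The share of entries affected, and the size and direction of any bias, cannot be derived from the documents. Nor do the documents show that back-filling will be common. How far the early scores drive the primary result is also unclear, because Section 4.1 speaks of the pre-to-postoperative difference after 14 days. This is an inexpensive weakness to repair in the primary data, not a fatal flaw.

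**What to change.** **Sections 7.1.1 and 7.2.** Have the caller enter in REDCap, with date and time, that day's pain score, the pills taken since the last call, and whether the diary entry had already been made. Asking for pills since the last call lets the next successful call cover a missed one.

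**Section 10.1.2, acceptance sentence.** State that the call value is used when the diary entry is absent or had not yet been made at the call. Flag diary entries first made after their own day, and run a sensitivity analysis that excludes them. Where no call was completed, mark the timing of that entry as unknown.

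**Section 10.1.2, removal sentence.** Amend it in the same revision, so that an isolated missing or late entry does not remove the whole patient and the available daily values are analysed. Without this, excluding late entries would turn them into gaps and remove whole patients from arms of 10.

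**Cost.** One short form and a little extra time on calls already planned. Some scores would come by telephone rather than from the diary, so the data set should carry the source of each value, and the protocol should say whether callers know the allocation.

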13.1 Ethical Standard

The investigator will ensure that this study is conducted in full conformity with Regulations for the Protection of Human Subjects of Research codified in 45 CFR Part 46, 21 CFR Part 50, 21 CFR Part 56, and/or the ICH E6.

13.2 Institutional Review Board

The protocol, informed consent form and all participant materials will be submitted to the IRB for review and approval. Approval of both the protocol and the consent form must be obtained before any participant is enrolled. Any amendment to the protocol will require review and approval by the IRB before the changes are implemented to the study. All changes to the consent form will be IRB approved; a determination will be made regarding whether previously consented participants need to be re-consented.

CONFIDENTIAL

This material is the property of the NYU School of Medicine and Langone Medical Center. Do not disclose or use except as authorized in writing by the study sponsor
Interventional Template Version: 11 January 2019

13.3 Informed Consent Process

13.3.1 Consent and Other Informational Documents Provided to Participants

Consent forms describing in detail the study agents, study procedures, and risks are given to the participant and written documentation of informed consent is required prior to starting intervention/administering study product.

13.3.2 Consent Procedures and Documentation

The informed consent process begins during the initial consultation visit for hand surgery, which is scheduled up to 3 months prior to the scheduled surgery. Informed consent can be obtained up until the day before the scheduled surgery.

Informed consent is a process that is initiated prior to the individual's agreeing to participate in the study and continues throughout the individual's study participation. Extensive discussion of risks and possible benefits of participation will be provided to the participants and their families. Consent forms will be IRB-approved and the participant will be asked to read and review the document. The investigator will explain the research study to the participant and answer any questions that may arise. All participants will receive a verbal explanation in terms suited to their comprehension of the purposes, procedures, and potential risks of the study and of their rights as research participants. Participants will have the opportunity to carefully review the written consent form and ask questions prior to signing. The participants should have the opportunity to discuss the study with their family or think about it prior to agreeing to participate. The participant will sign the informed consent document prior to any procedures being done specifically for the study. The participants may withdraw consent at any time throughout the course of the trial. A copy of the signed informed consent document will be given to the participants for their records. The rights and welfare of the participants will be protected by emphasizing to them that the quality of their medical care will not be adversely affected if they decline to participate in this study.

A copy of the signed informed consent document will be stored in the subject's research record. The consent process, including the name of the individual obtaining consent, will be thoroughly documented in the subject's research record.

13.4 Participant and Data Confidentiality

Information about study subjects will be kept confidential and managed according to the requirements of the Health Insurance Portability and Accountability Act of 1996 (HIPAA). Those regulations require a signed subject authorization informing the subject of the following:

- What protected health information (PHI) will be collected from subjects in this study
- Who will have access to that information and why
- Who will use or disclose that information
- The rights of a research subject to revoke their authorization for use of their PHI.

In the event that a subject revokes authorization to collect or use PHI, the investigator, by regulation, retains the ability to use all information collected prior to the revocation of subject authorization. For subjects that have revoked authorization to collect or use PHI, attempts should be made to obtain permission to collect at least vital status (i.e. that the subject is alive) at the end of their scheduled study period.

Participant confidentiality is strictly held in trust by the participating investigators, their staff, and the sponsor(s) and their agents. This confidentiality is extended to cover testing of biological samples and genetic tests in addition to the clinical information relating to participants. Therefore, the study protocol, documentation, data, and all other information generated will be held in strict confidence. No information concerning the study or the data will be released to any unauthorized third party without prior written approval of the sponsor.

CONFIDENTIAL

This material is the property of the NYU School of Medicine and Langone Medical Center. Do not disclose or use except as authorized in writing by the study sponsor
Interventional Template Version: 11 January 2019

Representatives of the IRB may inspect all documents and records required to be maintained by the investigator, including but not limited to, medical records (office, clinic, or hospital) and pharmacy records for the participants in this study. The clinical study site will permit access to such records.

The study participant's contact information will be securely stored at each clinical site for internal use during the study. At the end of the study, all records will continue to be kept in a secure location for as long a period as dictated by local IRB and Institutional regulations.

Study participant research data, which is for purposes of statistical analysis and scientific reporting, will be transmitted to and stored at NYU Langone Medical Center. This will not include the participant's contact or identifying information. Rather, individual participants and their research data will be identified by a unique study identification number. The study data entry and study management system used by NYU Langone Medical Center research staff, REDCap, will be secured and password protected. At the end of the study, all study databases will be de-identified and archived at the NYU Langone Medical Center.

14 Data Handling and Record Keeping

14.1 Data Collection and Management Responsibilities

Data collection is the responsibility of the clinical trial staff at the site under the supervision of the site PI. The investigator is responsible for ensuring the accuracy, completeness, legibility, and timeliness of the data reported.

All source documents should be completed in a neat, legible manner to ensure accurate interpretation of data. Black ink is required to ensure clarity of reproduced copies. When making changes or corrections, cross out the original entry with a single line, and initial and date the change. DO NOT ERASE, OVERWRITE, OR USE CORRECTION FLUID OR TAPE ON THE ORIGINAL.

Study data will be entered by the study team into HIPAA compliant, encrypted REDCap managed by MCIT. Patient binders containing signed ICFs and completed pain logs, as well as any other paper source documentation and/or CRFs, will be stored in a locked filing cabinet accessible only to the study team.

14.2 Study Records Retention

Study documents will be retained for the longer of 3 years after close-out, 5 years after final reporting/publication, or 2 years after the last approval of a marketing application is approved for the drug for the indication for which it is being investigated or 2 years after the investigation is discontinued and FDA is notified if no application is to be filed or if the application has not been approved for such indication. No records will be destroyed without the written consent of the sponsor, if applicable. It is the responsibility of the sponsor to inform the investigator when these documents no longer need to be retained.

